To evaluate the risk of developing EFAD in pediatric patients, including neonates, receiving either Clinolipid or standard-of-care soybean oil-based lipid emulsion (Intralipid) as a component of parenteral nutrition (PN) within the hospital setting from 7 to 90 days, inclusive.

EFAD will be defined using the Holman Index (plasma triene:tetraene ratio, specifically 5,8,11eicosatrienoic acid [mead acid] to 5,8,11,14 eicosatetraenoic acid [arachidonic acid, ARA] ratio) value of >0.4.

- 1. Secondary Objective(s):
- 2. The secondary objectives are as follows:
- 3. To evaluate the risk of developing liver disease, including parenteral nutrition-associated liver disease (PNALD) as defined by direct bilirubin ≥2 mg/dL when no other etiology for liver dysfunction is present in patients receiving with intravenous lipid emulsion (ILE)
- 4. To evaluate the adequacy of nutritional intervention in patients receiving either ILE
- 5. To evaluate the safety profiles of Clinolipid and Intralipid, as assessed by adverse events (AEs), serious adverse events (SAEs) and AEs of special interest (AESIs)

Study Design:

This will be a descriptive study designed to evaluate the risk for pediatric patients treated adequately with Clinolipid in the hospital for up to a maximum of 90 days to develop EFAD.

Additionally, this study design will evaluate the safety and efficacy of using Clinolipid in a pediatric population.

A randomized, double-blind study is appropriate to decrease clinician and patient bias during study conduct.

Approximately 100 pediatric patients, including neonates, will participate in the study. Patients will be randomized in a 1:1 ratio to the treatment groups (Clinolipid or Intralipid) according to a central dynamic randomization scheme stratified by site and age group (premature infants born <37 weeks of gestation (up to 1 month corrected age [CA]), full-term neonates born \geq 37 weeks of gestation to <1 month of age, infants 1 to <12 months of age, children 1 to <10 years of age, adolescent 10 to <18 years of age).

The primary and secondary objectives will be determined based on, but not limited to, the following clinical and laboratory assessments:

- Plasma fatty acid (FA) profiles and Holman Index;
- Genetic polymorphisms in the FA desaturase genes FADS1 and FADS2 in a subset of patients (approximately 20%);
- Hepatic function tests including alkaline phosphatase (ALP), aspartate aminotransferase (AST), alanine aminotransferase (ALT), gamma-glutamyl transferase (GGT), total and direct bilirubin to assess hepatic function and integrity;
- Plasma phytosterol (stigmasterol, campesterol, and sitosterol), cholesterol and squalene levels to determine potential correlation with the development of PNALD;
- Holman Index and fatty acid profiles will be evaluated. Select polymorphisms in the fatty acid desaturase genes, FADS1 and FADS2, will be determined in a subset of patients. The major plasma phytosterols found in the lipid emulsions (stigmasterol, campesterol, and sitosterol), cholesterol, and squalene also will be assessed.

After end of study treatment (maximum of 90 days), the patient will resume PN therapy as prescribed by their healthcare provider.

Study Population:

Key Inclusion Criteria:

- 1. Patients who are expected to require PN for at least 7 days;
- Premature infants (born at 24 to <37 weeks of gestation with a birth weight ≥750 g) must require at least 80% of targeted energy requirements by PN at study entry (up to 1 month CA); full term infants and children must require at least 70% of targeted energy requirements by PN at entry into the study;
- 3. A patient, or legal representative, has signed a written informed consent form per 21 CFR Part 50.55(e).

Key Exclusion Criteria:

- 1. Patients who are not expected to survive hospitalization or with a severe critical unresponsive illness at time of initiation with foreseeable intercurrent events that could jeopardize the patient's participation in the study (i.e. unresponsive shock, sepsis, renal failure requiring dialysis, severe unresponsive metabolic acidosis, and/or severe unresponsive metabolic disorders), as judged by the Investigator;
- 2. Patients with a known hypersensitivity to lipid emulsion, egg or soybean proteins, or any of the active substances, excipients, or components of the container or who have a history of an adverse event due to ILE;

- 3. Patients with liver disease including cholestasis;
- 4. Patients with severe hyperlipidemia or severe disorders of lipid metabolism characterized by hypertriglyceridemia (i.e. triglyceride >400 mg/dL);
- 5. Premature infants born <24 weeks of gestation and patients ≥ 18 years;
- 6. Patient requires or is expected to require propofol for sedation;
- 7. Patient, born to a symptomatic mother diagnosed with COVID-19 at the time of birth or before birth;
- 8. Patient has received a diagnosis of COVID-19 (diagnosis <2 months prior and/or symptoms have not resolved);
- 9. Female patients who are pregnant. Note: All female patients ≥12 years of age must have a negative urine human chorionic gonadotropin (hCG) pregnancy test at screening. For female patients <12 years of age, a urine hCG test at screening will be performed at the discretion of the investigator based on childbearing potential.

Test Product: Clinolipid (lipid injectable emulsion, USP) 20%

Reference Therapy: Intralipid (lipid injectable emulsion, USP) 20%

Mode of Administration: The dosing schedule is the same for each of the injectable lipid emulsions (ILEs), Clinolipid and Intralipid (control).

Table 1. Dosing Schedule for Intravenous Lipid Emulsions (g/kg/d of lipid) ^a				
	Day 1 of PN ^b (g/kg/day)	Targeted daily advancement rate (g/kg/day)	Maintenance ^c (g/kg/day)	Maximum (g/kg/day)
Preterm infants	1	1	2.5 to 3	3
Term infants (0-<1y)	1	1	2.5 to 3	3
Children (1-<10y)	1	1	2 to 3	3
Adolescents (10-<18y)	1	1	1 to 2	3

^a Daily administration over 20-24 hours

- ^b Randomization is recommended within 24 hours of signing consent but must occur within 3 days of signing consent. If patient is not randomized within 24 hours of informed consent, patient should be started on standard of care ILE on Day 1 of PN and transitioned to study drug once randomization has occurred.
- ^c Unless there is a clinical reason to decrease the dose in the opinion of the Investigator

Duration of Treatment: from 7 days, up to 90 days

Statistical Methods:

Determination of Sample Size:

The sample size of 100 patients (50 in each of the 2 treatment groups: Clinolipid vs Intralipid), including neonates, is based on the feasibility of timely enrollment of patients for generating reference data and summary descriptive statistics, rather than on a formal power calculation.

Analysis Sets:

The analysis sets in this study include: the Full Analysis Set (FAS), the Per Protocol Set (PPS), and the Safety Analysis Set. The FAS includes all patients who are randomized to receive either Clinolipid or standard-of-care (SOC) soybean oil-based lipid emulsion (Intralipid), consistent with the intention-to-treat principle. The PPS includes a subset of patients in the FAS who have Holman Index measurements taken at baseline and at least 1 other time point post-baseline, who have received a minimum of 7 days

of ILE treatment, and do not have a major protocol violation that potentially impacts the primary endpoint. The Safety Analysis Set includes all patients that have received treatment (Clinolipid or SOC).

Subgroup analyses of patients by age group (premature infants born <37 weeks of gestation (up to 1 month CA), full-term neonates born \geq 37 weeks of gestation <1 month of age, infants 1 to <12 months of age, children 1 to <10 years of age, adolescent 10 to <18 years of age) and subgroup analyses according to gestational age and birth weight will be conducted.

The primary endpoint analysis and secondary endpoint analyses of the development of liver disease including parenteral nutrition-associated liver disease (PNALD) and the adequacy of nutritional intervention will be conducted for both the FAS and PPS. The safety analyses (secondary endpoint no. 3) will be conducted for the FAS.

Primary Endpoint:

The risk of developing EFAD (determined by Holman Index value >0.4) in pediatric patients will be summarized by treatment group as frequency and percentage, Time to developing EFAD will be analyzed using the Kaplan-Meier approach. Both incidence rate and proportion of EFAD will be computed for each treatment group.

Holman Index also will be summarized with descriptive statistics (number of patients, mean, standard deviation, median, minimum, and maximum) on an approximately 15-day basis in each of the 2 treatment groups (Clinolipid vs Intralipid).

FA profiles will be summarized using descriptive statistics in each of the treatment groups.

FA profile, Holman Index will be assessed in the pediatric patients at baseline and approximately every 15 days throughout the study up to end of study treatment.

Genetic polymorphisms in the FA desaturase genes FADS1 and FADS2 will be assessed in a subset of patients (approximately 20%) and the distribution assessed in the context of the FA profile.

- Genetic material will be obtained from buccal smears in all patients that consent to analysis of FADS1 and FADS2 polymorphisms
- From the subset of patients consenting to genetic analysis, the 10 patients (5 Intralipid and 5 Clinolipid) with the lowest levels of ARA at any point during the study and the 10 patients (5 Intralipid and 5 Clinolipid) with the highest levels of ARA at any point during the study will be selected for analysis of single nucleotide polymorphisms within FADS1 and FADS2 genes as the synthesis of ARA from linoleic acid (LA) requires both the delta-5 and delta-6 desaturase enzymes (coded for by FADS1 and FADS2).
- Distribution of the polymorphisms within FADS1 and FADS2 genes will be assessed in the context various FA findings as the synthesis of gamma-LA and ARA from LA (n-6 pathway) and the synthesis of stearidonic acid, eicosapentaenoic acid (EPA) and docosahexaenoic acid (DHA) from ALA (n-3 pathway) require both the delta-5 and delta-6 desaturase enzymes (coded for by FADS1 and FADS2 genes).

Secondary Endpoints:

The 3 secondary endpoints of the study include 1) the development of liver disease including PNALD; 2) the adequacy of nutritional intervention; and 3) the safety profiles including AEs, SAEs and AESIs.

- 1. Liver disease, including development of PNALD
- The risk of developing PNALD (as defined by direct bilirubin ≥2 mg/dL when no other etiology for liver dysfunction is present in patients receiving ILE) in pediatric patients will be summarized by treatment group as frequency and percentage, as well as time to developing PNALD using the Kaplan-Meier approach. Both incidence rate and proportion of PNALD will be computed for each treatment group.
- To assess the relationship of phytosterol, cholesterol and squalene blood levels and the development of PNALD, plasma phytosterol, cholesterol, and squalene levels will be summarized using descriptive statistics at baseline, at the end of study treatment, and as well as maximal values during the study period in each of the 2 treatment groups. In addition, the correlations

between plasma phytosterol levels and direct bilirubin will be assessed by computing a Pearson's correlation coefficient or a Spearman correlation coefficient.

- Hepatic integrity (ALP, AST, ALT, GGT, total and direct bilirubin) will be evaluated by presenting descriptive summary statistics of individual values at different measurement time points from baseline to end of study treatment during the study period in each of the 2 treatment groups. Hepatic integrity parameters will also be summarized in shift tables comparing results from baseline to end of study treatment (max 90 days) and to maximal value during the study period in each of the 2 treatment groups. In addition, assessment for drug-induced liver injury will be conducted according to Hy's Law and eDISH criteria.^{1,2}
- 2. Adequacy of nutritional intervention

The adequacy of nutritional intervention in patients receiving either Clinolipid or Intralipid will be assessed and results analyzed as follows:

- Prescribed and actual nutritional intakes (calories, protein, lipids and carbohydrates) from both PN and enteral/oral nutrition will be collected and recorded on a daily basis and summarized daily for the first 2 weeks of treatment and on an approximately every 15-day basis afterwards up to the end of study treatment in each of the treatment groups.
- Growth will be assessed and evaluated from baseline to end of study treatment on an approximately every 15-day basis using descriptive summary statistics for weight, and height/length (and head circumference in infants <1 year) in each of the treatment groups as follows:
- Gain in weight (g/kg/day in infants and g/day in children and adolescents), and gain in length/height (mm/week in all) and head circumference (mm/week in infants <1 year);
- Changes in the standard deviation score (SDS or z-score) from reference growth curves (Fenton growth curve for premature infants, World Health Organization growth standards for infants and children ages 0 to 2 years, or Center for Disease Control growth charts for children age ≥2 years).
- 3. Safety profiles of Clinolipid and Intralipid, including AEs, SAEs and AESIs.

The safety profiles will be assessed and analyzed as follows:

- Vital signs and laboratory tests will be summarized using descriptive summary statistics in each of the 2 treatment groups.
- Additional neonatal morbidities including bronchopulmonary dysplasia (BPD), retinopathy of prematurity (ROP), intraventricular hemorrhage (IVH), periventricular leukomalacia (PVL), necrotizing enterocolitis (NEC), and late-onset sepsis in enrolled premature infants born <37 weeks of gestation up to 1 month CA.
- All AEs, SAEs, and AESI will be tabulated by body system using the Medical Dictionary for Regulatory Activities (MedDRA) coded terms.
- Adverse events and SAEs will be presented by treatment group using frequencies and percentages. In addition, the AE rate per 100 patient days will be reported.

Date of Original Approved Protocol: 2014 May 20

Amendment 1: 2014 June 20

Amendment 2: 2014 September 03

Amendment 3: 2015 May 26

Amendment 4: 2019 March 22

Amendment 5: 2020 April 13

Amendment 5.1: 2020 April 21

Amendment 5.2: 2020 June 01

Amendment 5.3: 2020 June 25

Amendment 5.4: 2020 August 26

Amendment 5.5: 2022 February 03

Amendment 5.6: 2022 February 22

Table of Contents

SYNOPSIS	3
LIST OF ABBREVIATIONS AND DEFINITIONS OF TERMS	13
1. INTRODUCTION	15
2. STUDY OBJECTIVES	18
2.1 Primary Objective	18
2.2 Secondary Objective(s)	19
3. INVESTIGATIONAL PLAN	20
3.1 Overall Study Design and Plan	20
3.2 Rationale for Study Design and Control Group	21
3.3 Study Duration	21
4. STUDY POPULATION SELECTION	21
4.1 Study Population	21
4.2 Inclusion Criteria	22
4.3 Exclusion Criteria	23
5. STUDY TREATMENT(S)	24
5.1 Description of Treatment(s) and Dosing	24

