2.2 Secondary Objective(s)

The secondary objectives in patients receiving either Clinolipid or Intralipid are to evaluate:

- The risk of developing liver disease including PNALD:
 - PNALD will be defined by direct bilirubin ≥2 mg/dL when no other etiology for liver dysfunction is present;
 - Hepatic integrity will be assessed by measuring plasma liver function tests: alkaline phosphatase (ALP), aspartate aminotransferase (AST), alanine aminotransferase (ALT), gamma-glutamyl transferase (GGT), and total and direct bilirubin;
 - Plasma main phytosterols (stigmasterol, campesterol, sitosterol), cholesterol and squalene levels will be assessed. Phytosterols levels will be correlated with the risk of developing PNALD.
- The adequacy of nutritional interventions:
 - Prescribed and actual nutritional intakes (energy, protein, carbohydrates, and lipid) from both PN and enteral/oral nutrition will be collected and recorded on a daily basis and summarized on a daily basis during the first 2 weeks of treatment and on an approximately 15-day basis afterwards up to the end of study treatment in each of the treatment groups.
 - Growth will be assessed and evaluated from baseline to end of study treatment on an approximately every 15-day basis using descriptive summary statistics for weight, and height/length (and head circumference in infant <1 year) in each of the treatment groups as follows:
 - Gain in weight (g/kg/day in infants <1 year of age, g/day in children and adolescents) and gain in length/height (mm/week in all) and head circumference (mm/week in infants <1 year);
 - Changes in the standard deviation score (SDS or z-score) from reference growth curves (Fenton growth curve for premature infants, World Health Organization (WHO) growth standards for infants and children ages 0 to 2 years, or Center for Disease Control (CDC) growth charts for children age ≥2 years).

- The safety profiles of Clinolipid and Intralipid, as assessed by adverse events (AEs), serious adverse events (SAEs) and AEs of special interest (AESIs)

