9.6.1.3 Plasma Phytosterol, Cholesterol, and Squalene Levels

Plasma phytosterol, cholesterol, and squalene levels will be summarized using descriptive statistics (mean, standard deviation, median, minimum, and maximum) at baseline and the end of study treatment, as well as maximal value during the study and the delay (days) between study baseline and maximal value in each of the 2 treatment groups (Clinolipid vs Intralipid). In addition, the correlations between plasma phytosterol levels and direct bilirubin values will be assessed by computing a Pearson's correlation coefficient or a Spearman correlation coefficient depending on whether the normality assumption is fulfilled.

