2.4.2.4 Plasma Phytosterols, Cholesterol, and Squalene Levels

Plasma phytosterols (stigmasterol, campesterol, and sitosterol), cholesterol, and squalene levels will be summarized using descriptive statistics (mean, standard deviation, Q1, median, Q3, minimum, and maximum) at baseline and the end of study treatment, as well as post-baseline maximal value during the study and the delay (days) between study baseline and post-baseline maximal value in each of the 2 treatment groups (Clinolipid vs Intralipid). In addition, the correlation between plasma phytosterol levels and direct bilirubin values will be assessed by computing a Pearson's correlation coefficient or a Spearman correlation coefficient depending on whether the normality assumption is fulfilled. Normality will be assessed visually with a QQ plot. Values will be paired by patient and visit. A scatterplot of plasma phytosterol and direct bilirubin values will also be produced with different symbols for each of the two different treatment groups.

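### The synopsis promises to relate phytosterols, cholesterol and squalene to developing PNALD, but no planned output compares patients with and without PNALD, and cholesterol and squalene get no association analysis

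*Protocol*

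**What the plan says.** The aim appears in two forms.

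- **All three analyte groups.** The synopsis lists phytosterol, "cholesterol and squalene levels to determine potential correlation with the development of PNALD" among its assessments. Under Secondary Endpoints it introduces the method with "To assess the relationship of phytosterol, cholesterol and squalene blood levels and the development of PNALD".
- **Phytosterols only.** Protocol 2.2 says that all three will be measured, but makes only the narrower promise "Phytosterols levels will be correlated with the risk of developing PNALD". SAP 1.3 and 1.6.2 repeat this.

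Two analyses are planned.

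- **Summaries.** Protocol 9.6.1.3 and SAP 2.4.2.4 give descriptive statistics for all three at baseline and end of treatment, plus "maximal value during the study and the delay (days) between study baseline and maximal value in each of the 2 treatment groups".
- **Association.** SAP 2.4.2.4 states that "the correlation between plasma phytosterol levels and direct bilirubin values will be assessed by computing a Pearson's correlation coefficient or a Spearman correlation coefficient". A normality check decides which of the two is used. It adds "Values will be paired by patient and visit", and "A scatterplot of plasma phytosterol and direct bilirubin values will also be produced with different symbols for each of the two different treatment groups".

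The SAP's PNALD analysis (2.4.2.2.2) contains no sterol variable. SAP section 3 declares no change from the protocol.

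**The concern.** The outcome named in the aim is PNALD, an event that a patient either develops or does not. A reader expects at least one output showing whether patients who develop it had different levels from those who do not. None is planned. For cholesterol and squalene there is no association measure of any kind, so carrying out the plan exactly leaves that part of the synopsis aim without a result. For phytosterols, the reader gets a correlation with the laboratory value behind PNALD. That is related to the question but is not the same question.

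A split made after unblinding would require someone to choose the sample (baseline, maximum, last before onset) with the data in view. Stating the choice now avoids that.

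**Working it through.** The plan gives no figure to reproduce here. The sample size of 100 rests on feasibility, and no PNALD rate is stated.

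**1. Aim against planned output**

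| Analyte | Aim: synopsis | Aim: Protocol 2.2, SAP 1.3 and 1.6.2 | Summary by arm (Table 14.3.6.3.1) | Correlation with direct bilirubin (Table and Figure 14.3.6.3.2) | Any output by PNALD status |
|---|---|---|---|---|---|
| Phytosterols | yes | yes | yes | yes | none |
| Cholesterol | yes | measured only | yes | none | none |
| Squalene | yes | measured only | yes | none | none |

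PNALD values (16.2.8.2.1) and sterol levels (16.2.8.2.4) are in separate listings. SAP 2.6.1 rules out covariate adjustment, so no model links them.

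**2. What the by-arm tables can show.** Protocol Table 2 gives the content of the emulsions in µg/mL:

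- Squalene: 387.45 in Clinolipid, 7.43 in Intralipid; 387.45 / 7.43 = 52-fold.
- Cholesterol: 109.70 and 274.08; 274.08 / 109.70 = 2.5-fold the other way.
- Total phytosterols: 274.38 and 439.07; 439.07 / 274.38 = 1.6-fold the other way.

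Plasma levels need not follow these ratios exactly, but an arm difference is expected whoever develops PNALD.

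**3. How good a proxy the bilirubin correlation is.** Suppose phytosterol is 1 SD higher in cases and a share p of patients are cases (both assumed). The correlation of phytosterol with PNALD status itself is

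r = √(pq) / √(1 + pq), with q = 1 − p.

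- p = 0.05: √0.0475 / √1.0475 = 0.21
- p = 0.15: √0.1275 / √1.1275 = 0.34

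A simulation used 100 patients with one value each, and assumed bilirubin unrelated to phytosterol below 2 mg/dL. It gave a mean Pearson coefficient with direct bilirubin of 0.20-0.32 over p = 0.05 to 0.15, and a Spearman of 0.08-0.20. Re-running it with a different assumed skewed bilirubin distribution gave Pearson 0.19-0.30 and Spearman 0.07-0.20. Pearson therefore loses little against PNALD status. Spearman loses more, but under an assumption that the documents neither support nor contradict.

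The correlation stays indirect for other reasons. Same-visit pairs do not show whether levels were raised before onset. The protocol definition of PNALD also requires that no other cause is present. The SAP does not say whether arms are pooled or how repeated pairs from one patient are handled.

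**4. Precision of a split by PNALD status.** The 95% half-width of a standardised mean difference is 1.96 × √(1/cases + 1/non-cases). With 50 per arm and assumed rates:

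- 5%: 2.5 against 47.5 gives 1.96 × √(0.400 + 0.021) = 1.27 SD
- 10%: 5 against 45 gives 1.96 × √(0.200 + 0.022) = 0.92 SD
- 15%: 7.5 against 42.5 gives 1.96 × √(0.133 + 0.024) = 0.78 SD

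**The case against.** The strongest defence is that the SAP derives PNALD from direct bilirubin alone, at 2 mg/dL or more (2.4.2.2.1). Correlating phytosterols with direct bilirubin then uses the defining variable without cutting it in two, and the scatterplot shows the levels that accompany values above the threshold. The formal objective in Protocol 2.2 ties only phytosterols to PNALD, and phytosterols do get an association analysis. The listings would permit a split later. All of this stands and lowers the severity. It does not supply an association result for cholesterol or squalene, or any output by PNALD status.

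Four stronger readings are tempting but not supported:

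- **That the secondary question cannot be addressed at all.** For phytosterols it is addressed indirectly, through the variable that defines PNALD.
- **That a real association would appear as near zero.** The Pearson values of 0.20-0.32 are close to the 0.21-0.34 obtained with PNALD status itself, so the low figure mainly reflects few cases. Only Spearman drops clearly, and that rests on an assumed bilirubin pattern.
- **That maxima, which rise with the number of samples, distort the association.** Maxima are only summarised by arm; the correlation uses same-visit pairs.
- **That the Day 15-75 samples go unused.** Pairing by visit brings the phytosterol values into the correlation and scatterplot, and listing 16.2.8.2.4 covers all three analyte groups.

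**Conclusion.** The aim and the analysis do not match. The synopsis aim for cholesterol and squalene has no association analysis, and the phytosterol aim is met only by proxy. No output for any analyte compares patients with and without PNALD. This follows from the text and shells alone and needs no assumption. The sizes in the working do rest on assumptions: a PNALD rate of 5-15%, a 1 SD difference between cases and non-cases, and a chosen bilirubin distribution.

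Severity is low to moderate. The study is descriptive, SAP 1.4.2 plans no hypothesis test, and this is a secondary objective. The primary endpoint is not affected.

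**What to change.** In SAP 2.4.2.4:

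1. Add to Table 14.3.6.3.1 a descriptive split of each phytosterol, cholesterol and squalene by PNALD status (yes/no) within arm. Show baseline for everyone. For cases, use samples taken before the first direct bilirubin of 2 mg/dL or more. Summarise non-cases at each scheduled visit while they are still free of PNALD. Matching non-cases to a single common visit would not be defined, because cases will have different onset visits.
2. Extend the direct bilirubin correlation (Table 14.3.6.3.2) and scatterplot (Figure 14.3.6.3.2) to cholesterol and squalene, and mark PNALD cases on the plots.
3. Keep the phytosterol-bilirubin correlation as planned.

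The minimum alternative is to reword the synopsis and Protocol 2.2 so that the aim is the analysis actually planned: phytosterols against direct bilirubin.

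The cost is SAP wording, added columns and further panels, from data already scheduled for collection. The drawback is imprecision: cases will be few, so the split should be presented as descriptive. For a patient whose PNALD arises by Day 15, the only pre-onset sample may be the baseline one.
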